#### 4.11.4 Clinical Laboratory Evaluation

Laboratory tests will be reported separately for hematology and blood chemistry.

For the purposes of presentation in both tables and listings, the following laboratory test results will be converted to the International System of Units (SI) before presentation: sodium, potassium, chloride, bicarbonate (or CO2), albumin, total protein, creatinine, uric acid, calcium, phosphorus, magnesium, glucose, total and direct bilirubin, alkaline phosphatase, red blood cell (RBC) count, hemoglobin, hematocrit, platelets, white blood cell count with 5-part differential

performed manually or by flow cytometry (lymphocytes, neutrophils, monocytes, basophils, and eosinophils), amylase, lipase, alanine aminotransferase (ALT), and aspartate aminotransferase (AST). Laboratory tests will be graded according to CTCAE Version 5.0 or higher.

If a laboratory test value is reported using a non-numeric qualifier (e.g., less than [<] a certain value or greater than [>] a certain value), the given numeric value will be used in the summary statistics, ignoring the non-numeric qualifier.

For laboratory tests graded by CTCAE, the following summary tables will be created by treatment arm:

- Summary of worst post-baseline value on treatment, regardless of baseline value according to the following categories:
  - Any grade
  - Grades 1 - 2
  - Grades 3 - 4
  - Grade 3
  - Grade 4
- Summary of worst post-baseline value on treatment that represents a worsening in grade from baseline according to the following categories:
  - Any grade
  - Grades 1 - 2
  - Grades 3 - 4
  - Grade 3
  - Grade 4

Laboratory tests with bi-directional grades (e.g., hyperglycemia and hypoglycemia) will be presented separately for each direction within each summary table.

For laboratory tests not graded by CTCAE, the following summary tables will be created by treatment arm:

- Summary of worst post-baseline value on treatment, regardless of baseline value according to the following categories:
  - Low (less than lower limit of normal)
  - Normal (greater than or equal to lower limit of normal and less than or equal to upper limit of normal)
  - High (greater than upper limit of normal)
- Summary of worst post-baseline value on treatment that represents a worsening from baseline according to the following categories:
  - Low (less than lower limit of normal)
  - Normal (greater than or equal to lower limit of normal and less than or equal to upper limit of normal)
  - High (greater than upper limit of normal)

A subject will be defined as having a treatment-emergent laboratory abnormality if any of the following conditions are satisfied for a specific laboratory parameter:

- Laboratory result within the normal range at baseline and either a result below the lower limit of the normal range or above the upper limit of the normal range at any post-baseline time point on or before 30 days after the last dose of duvelisib.
- Laboratory result below the lower limit of the normal range at baseline and a laboratory result above the upper limit of the normal range at any post-baseline time point on or before 30 days after the last dose of duvelisib.
- Laboratory result above the upper limit of the normal range at baseline and a laboratory result below the lower limit of the normal range at any post-baseline time point on or before 30 days after the last dose of duvelisib.

A by-subject listing of all laboratory data will be provided by treatment group, with abnormal values flagged, and include center, subject identifier, age, sex, race, weight and visit. Laboratory reference ranges will also be listed.

Laboratory values (hematology, biochemistry and urinalysis) will be listed by subject and study time point including changes from baseline (with the exception of urinalysis). Baseline will be defined as described in [Section 4.2](#).

All values outside the clinical reference ranges will be flagged in the data listings. The abnormal values will be flagged with 'L' for values below the lower limit of the clinical reference range and 'H' for values above the upper limit of the clinical reference range and included in the listings. The Investigator will assess whether the values outside the clinical reference range are clinically significant and these will be reported as abnormal not clinically significant (NCS) or abnormal clinically significant (CS). Clinically significant laboratory values will be recorded by the Investigator as AEs.

Descriptive statistics (for non-categorical data including hematology and biochemistry) will be presented by cohort for both individual values (N, mean, SD, median, minimum, and maximum) and changes from baseline.

Boxplots over time (at each scheduled visit) will be provided for each laboratory parameter.

#### **4.11.5 Vital Signs, Physical Findings and Other Observations Related to Safety.**

##### **4.11.5.1 Vital Signs**

The actual values of vital sign parameters, including temperature, heart rate, weight and systolic and diastolic BP, will be presented in a by-subject listing. Vital sign parameter reference ranges will also be listed.

Blood pressure will be summarized as follows by treatment arm:

- Descriptive statistics, for systolic and diastolic BP separately
  - Baseline value
  - Maximum on-treatment value
  - Change from baseline to maximum on-treatment value

- Categorical summary of baseline value, maximum on-treatment value for systolic and diastolic BP separately, with categories defined as follows:
  - Diastolic BP
    - < 80 mm Hg
    - ≥ 80 – 89 mm Hg
    - ≥ 90 mm Hg
  - Systolic BP
    - < 120 mm Hg
    - ≥ 120 – 129 mm Hg
    - ≥ 130 – 139 mm Hg
    - ≥ 140 mm Hg
- Categorical summary of baseline value, maximum on-treatment value for systolic and diastolic BP combined using the categories defined above (i.e., diastolic <80 mm Hg and systolic <120 mm Hg, diastolic <80 mm Hg and systolic 120 – 129 mm Hg)

Heart rate will be summarized as follows by treatment arm:

- Descriptive statistics for baseline value, minimum on-treatment value, maximum on-treatment value, change from baseline to maximum on-treatment value
- Categorical summary of baseline value, minimum on-treatment value, maximum on-treatment value, with categories defined as follows:
  - < 60 bpm
  - ≥ 60 – 100 bpm
  - > 100 bpm

Boxplots over time (at each scheduled visit) will be provided for each BP and heart rate measured.

#### 4.11.5.2 ECG, ECHO/MUGA, and Physical Examinations

Per protocol, ECGs, ECHO/MUGA results, and full physical examinations findings are to be collected at baseline only. By-subject listing will be provided for each of these parameters.

#### 4.11.6 Safety Monitoring

No data monitoring committee will be set up for monitoring the safety of study treatment.

### 4.12 Other Analyses

#### 4.12.1 Pharmacokinetics

The PK data collected will be analyzed by standard population PK methods, using appropriate software. The intent of this analysis is to characterize the parameters of PK disposition.

Additional exploration of the relationship between duvelisib exposure and safety or efficacy assessments may be completed. If there is only a limited amount of plasma concentration data

from this study, the data may be pooled with the results of other studies to perform the population PK analysis. A separate PK analysis plan may be developed.

#### 4.12.2 Quality of Life (QoL)

##### 4.12.2.1 ECOG Performance Status

Summaries of ECOG performance status will be presented by visit. Shift tables for change in

ECOG performance score from baseline by worst post-baseline score will be produced.

A by-subject listing of ECOG performance status data will be provided.

##### 4.12.2.2 EQ-5D-3L Scores

The EQ-5D-3L contains a descriptive system with one response for each of the 5 dimensions (mobility, self-care, usual activities, pain/discomfort, and anxiety/depression). The first response is coded as 1 (indicating no problems), the second response is coded as a 2 (indicating some problems), and the third response is coded as a 3 (indicating extreme problems). Ambiguous responses (e.g., more than one response in a dimension, if applicable) are treated as missing values. The EQ-5D also contains a Visual Analog Scale (VAS) for health state ranging from 0 to 100, where 0 represents worst imaginable health state and 100 represents the best imaginable health state. Ambiguous values (the line crosses the VAS twice) should be treated as missing values.

For each dimension of the descriptive system, the number and percentage of subjects with no problems, some problems, and extreme problems will be reported at each visit.

Summary statistics for the VAS of health state and the changes from baseline will be reported for each visit. By-subject listing of these data will be provided.

Also refer to the [EQ-5D-3L user guide](#) [4] for additional considerations.

#### 4.12.3 Other Exploratory Analyses

The other exploratory endpoints, including biomarker endpoints, will be summarized descriptively. A separate analysis plan may be developed for formal analyses.

### 4.13 Determination of Sample Size

The sample size for each arm was calculated using a 2-stage approach.

For each arm: in Stage 1, 15 subjects will be randomized. The evaluation of the first stage will take place after the 15 enrolled subjects have been followed for a minimum of 3 cycles (18 weeks).

If there are fewer than 6 responders (PR or CR) among the first 15 subjects, consideration may be given to terminate the treatment arm. The decision to proceed to Stage 2 will be based on the totality of data observed, including types of responses, safety data, and discontinuation rates. The treatment arm may also not proceed to Stage 2 if the totality of the data is viewed as compelling;

such scenarios could include (but are not limited to) accumulating enough data in Stage 1 to conclude the ORR exceeds 30%. If the treatment arm proceeds to Stage 2, up to 36 additional subjects will be enrolled for a total of 51. If fewer than 22 (43%) responders (PR or CR) are observed in 51 subjects, consideration may be given to conclude that the treatment schedule does not warrant further study in this population. The final evaluation of each schedule will be based on the totality of data observed, including types of responses, safety data, and discontinuation rates. This design yields a type I error rate of 0.025 (1-sided) and power of 90% under the assumptions described above.

Subjects will be stratified by number of prior therapies (1 or  $> 1$ ), bulky disease status (longest diameter of baseline lesion  $< 5$  cm or  $\geq 5$  cm) and time since last recurrence ( $\geq 24$  months or  $< 24$  months).

Note: "Enrolled" means subjects', or their legally acceptable representative's, agreement to participate in a clinical study following completion of the informed consent process. Potential subjects who are pre-screened for the purpose of determining eligibility for the study but do not sign an informed consent form (ICF) are not considered enrolled.

#### 4.14 Changes in the Conduct of the Study or Planned Analysis

Additional analyses not specified in this SAP may be conducted, if necessary. In such cases, a separate analysis plan will be created to document such analyses. The SAP will be updated as necessary if the protocol is amended.

**6 APPENDIX****Appendix 1: List of Preferred Terms for Adverse Events of Special Interest**

Grouped Term	Preferred Terms
All infections (excluding Pneumonia and COVID-19 infections)	All preferred terms under SOC = 'Infections Infections and infestations' excluding any preferred term containing the word 'pneumonia' and excluding any preferred terms included in the COVID-19 infections Grouped Term.
Diarrhea	Diarrhoea, Diarrhoea hemorrhagic, Defecation urgency
Colitis	Colitis, Colitis erosive, Enterocolitis, Enterocolitis hemorrhagic, Colitis microscopic, Necrotising colitis, Colitis ulcerative
Pneumonia	Pneumonia, any PT containing the word/string "pneumonia" except for "Pneumonia aspiration", Atypical pneumonia, Atypical mycobacterial pneumonia, Bronchopneumonia, Bronchopulmonary aspergillosis
Pneumonitis	Pneumonitis, Interstitial lung disease, lung infiltration, acute interstitial pneumonitis
Transaminase elevation	Alanine aminotransferase increased, Aspartate aminotransferase increased, Transaminases increased, Hypertransaminasaemia, Hepatic enzyme increased, Acute hepatic failure, Drug-induced liver injury, Hepatic failure, Hepatocellular injury, Hepatotoxicity
Cutaneous reactions	Dermatitis, Dermatitis allergic, Dermatitis bullous, Dermatitis exfoliative, Dermatitis psoriasiform, Drug eruption, Drug reaction with eosinophilia and systemic symptoms, Erythema, Erythema multiforme, Generalised erythema, Exfoliative rash, Rash, Rash generalised, Rash erythematous, Rash follicular, Rash macular, Rash maculo-papular, Rash maculovesicular, Rash papular, Rash papulosquamous, Rash pruritic, Rash pustular, Rash vesicular, Toxic skin eruption, Palmar erythema, Palmoplantar keratoderma, Palmar-plantar erythrodysesthesia syndrome, Perivascular dermatitis, Skin reaction, skin toxicity, Stevens-Johnson syndrome, Toxic epidermal necrolysis
Neutropenia	Neutropenia, Neutrophil count decreased
COVID-19 infections	Asymptomatic COVID-19, Congenital COVID-19, Coronavirus infection, Coronavirus test positive, COVID-19 pneumonia, COVID-19 treatment, Multisystem inflammatory syndrome in children, Post-acute COVID-19 syndrome, SARS-CoV-2 RNA decreased, SARS-CoV-2 RNA fluctuation, SARS-CoV-2 RNA increased, SARS-CoV-2 sepsis, SARS-CoV-2 test false negative, SARS-CoV-2 test positive, SARS-CoV-2 viraemia, Suspected COVID-19, Vaccine derived SARS-CoV-2 infection

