#### 4.11.2.1 Other Adverse Events of Interest

Selected MedDRA PTs will be combined to create grouped PTs or categories to further characterize risks associated with duvelisib. The following risks will be summarized as Adverse Event of Special Interest:

- Diarrhea/colitis
- Infections
  - All infections, excluding Pneumonia and COVID-19 infections
  - Pneumonia
  - COVID-19 infections
- Cutaneous reactions
- Non-infectious pneumonitis
- Neutropenia
- Hepatotoxicity (as defined by transaminase elevations)

The specific PTs that will be combined for each risk are defined in [Appendix 1](#).

For each risk, PTs will be summarized at the grouped PT and individual PT (and grouped SOC if applicable), at the subject level:

- TEAEs (all grades, all causalities)
- Treatment-related TEAEs (all grades)
- Grade 1 or 2 only TEAEs (all causalities)
- Grade 3 or higher TEAEs (all causalities)
- Treatment-emergent SAEs (all causalities)
- TEAEs resulting in dose holds
- TEAEs resulting in dose reductions
- TEAEs resulting in dose holds or reductions
- TEAEs resulting in discontinuation of study drug (all causalities)
- Time to initial onset (defined as AE start date – first dose date + 1)

In addition, the following summaries will be created for each grouped PT within each grouped SOC, at the event level:

- Summary of dose modifications
  - Number of events resulting in dose holds
  - Number of events resulting in dose reductions
  - Number of events resulting in dose holds or reductions
  - Number of events resulting in discontinuation of study drug
- Summary of outcome
  - Number of events resolved
  - Number of events resolved with sequelae
  - Number of events resolved or resolved with sequelae
  - Number of events not resolved
- Duration of AE

- Concomitant medications used to treat AEs (a specific list of concomitant medications associated with each risk will be provided)

For each subject and each AE, the worst severity recorded will be attributed and used in the by-severity summaries. Similarly, the worst causality (most related to treatment) will be attributed and used in the by-causality summaries. If causality is missing, the worst case will be assumed (related to treatment).

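### The lung and infection AESI groups in SAP Appendix 1 do not separate as SAP 4.11.2.1 labels them: one term meets two definitions, a second may, and the Pneumonia string rule has no SOC limit

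*SAP*

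**What the plan says.** SAP 4.11.2.1 lists the risks to be summarized as adverse events of special interest. Under Infections it has three sub-items: a residual row labelled "All infections, excluding Pneumonia and COVID-19 infections", a Pneumonia row and a COVID-19 row. "Non-infectious pneumonitis" is a separate risk, outside Infections.

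SAP Appendix 1 gives the membership rules:

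- **Pneumonia:** the term *Pneumonia* itself, then "any PT containing the word/string 'pneumonia' except for 'Pneumonia aspiration", then "Atypical pneumonia, Atypical mycobacterial pneumonia, Bronchopneumonia, Bronchopulmonary aspergillosis". There is no SOC restriction and no COVID-19 exclusion.
- **COVID-19 infections:** a fixed list of 17 terms, including "Coronavirus test positive, COVID-19 pneumonia, COVID-19 treatment".
- **All infections (residual):** terms in the infections SOC, "excluding any preferred term containing the word 'pneumonia" and "excluding any preferred terms included in the COVID-19 infections Grouped Term".
- **Pneumonitis:** a closed list, "Pneumonitis, Interstitial lung disease, lung infiltration, acute interstitial pneumonitis".

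The SAP Revision History shows that the COVID-19 AESI was added at version 2.1 (19 May 2023).

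**The concern.** The labels in 4.11.2.1 promise a residual row free of pneumonia and COVID-19, and a pneumonitis risk kept apart from infection. The Appendix 1 rules do not deliver this, because they mix three devices: a text string, a list of named terms, and an SOC. The residual row excludes COVID-19 by group membership but excludes pneumonia by a word. The Pneumonia row excludes neither COVID-19 nor non-infectious terms.

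The grouping feeds every AESI summary in 4.11.2.1. At subject level these are all-grade, treatment-related, Grade 1 or 2, Grade 3 or higher, serious, dose hold, dose reduction, discontinuation and time to onset. At event level they are dose modification, outcome, duration and concomitant medication. Protocol 2.3.1 names infections and pneumonitis as separate identified risks, and Protocol 4.2 asks whether the holidays reduce the frequency, severity or duration of adverse events. A sorting error between these rows therefore bears on a question the study was set up to describe.

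**Working it through.** The SAP states no figure to reproduce. The check is to put each relevant term through the Appendix 1 rules and see which rows it meets.

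**Main reading.** The terms after the aspiration exception are additions to Pneumonia, and a term contains the word if it contains the string.

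| Term | Assumed SOC | Rows met |
|---|---|---|
| *Pneumonia*, *Atypical pneumonia*, *Atypical mycobacterial pneumonia*, *Bronchopneumonia* | Infections | Pneumonia |
| *COVID-19 pneumonia* | Infections | Pneumonia **and** COVID-19 |
| *Bronchopulmonary aspergillosis* | Infections | Pneumonia **and** All infections |
| *Pneumonia aspiration* | Either | None of the four |
| Any other term containing pneumonia | Not infections | Pneumonia, not Pneumonitis |
| The four listed Pneumonitis terms | Not infections | Pneumonitis |

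**Step 1, COVID-19 pneumonia.** Of the 17 COVID-19 terms, 1 contains the string. It is not the excepted term, so it is in Pneumonia; it is listed, so it is in COVID-19. The residual row has a clause removing COVID-19 members. The Pneumonia row has no such clause, and nothing elsewhere gives a precedence.

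**Step 2, aspergillosis.** The term enters Pneumonia by name. It lacks the string, so the residual row's exclusion does not remove it. If it is coded to the infections SOC, it stays in a row labelled as excluding Pneumonia.

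**Step 3, no SOC limit.** The string rule applies to any term in any SOC, yet 4.11.2.1 places the row under Infections. None of the four Pneumonitis terms contains the string pneumonia, and that list is closed. A non-infectious term containing pneumonia, other than the aspiration term, therefore goes to Infections and cannot reach Pneumonitis.

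**Sensitivity to reading.**

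- If the named terms are read as further exceptions, steps 1 and 3 are unchanged. Aspergillosis then falls only in All infections. This reading is strained: excepting a term that lacks the string does nothing, and under string matching it leaves *Atypical pneumonia*, *Atypical mycobacterial pneumonia* and *Bronchopneumonia* in no row.
- If word in the residual row means a whole word, *Bronchopneumonia* joins aspergillosis in both Pneumonia and All infections on the main reading.

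**Scale.** With 51 subjects per arm (SAP 4.13), one subject is 1/51 = 1.96 percentage points. For orientation only, Protocol 2.3.1 reports pneumonia in 21.6% of 588 earlier monotherapy subjects. At that rate an arm would have 0.216 × 51 = 11.0 subjects, and one more would move the row from 11/51 = 21.6% to 12/51 = 23.5%.

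**The case against.** **Overlap need not be an error.** Only the residual row is labelled as excluding the others. Nothing says Pneumonia and COVID-19 are mutually exclusive or will be added together, and *COVID-19 pneumonia* is both things. This stands. A reader might infer that the event wrongly inflates the Pneumonia row; the documents do not support that, and removing it is a choice, not the only correct answer. What remains is that the overlap is undeclared.

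**Two of the three points depend on coding that the documents do not give.** The SOC of *Bronchopulmonary aspergillosis* is not stated, and the only term either document singles out from the string rule is the aspiration term. This also stands: points 2 and 3 are conditional. The rules themselves are explicit, however, and would mis-sort such terms if they occur.

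**The errors can be traced.** SAP 4.11.2.1 shows individual preferred terms beneath each group, SAP 4.11.2 tabulates events by SOC and preferred term, and the listings carry the SOC, preferred term and verbatim term. A careful reader could rebuild the counts. That makes the problem visible but does not correct the grouped counts.

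**The consequence is small.** The tables are descriptive, Protocol 9.4.1 plans no formal testing beyond ORR and no formal comparison between arms, and no decision rule uses an AESI row alone. This stands and limits the weight of the point.

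**Pneumonia is not a separate identified risk.** A reader might infer that pneumonia and pneumonitis are separate identified risks, each with its own management row. Protocol 2.3.1 lists infections and pneumonitis, and Protocol Table 5 has Infections and non-infectious Pneumonitis entries but no general pneumonia row. The distinction at stake is infection against pneumonitis.

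**Conclusion.** The point holds as a defect in the grouping rules, confined to descriptive AESI tables. The double membership of *COVID-19 pneumonia* is certain under every reading. The aspergillosis overlap rests on the natural reading of the appendix and on coding to the infections SOC. The capture of non-infectious terms follows from the missing SOC limit, and bites only if such a term is reported.

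Each subject counted in a second row, or moved between rows, changes a row by about 2.0 percentage points of 51. For *COVID-19 pneumonia* the addition to the Pneumonia row can be smaller, since a subject with another pneumonia event is already counted there. The number of subjects affected cannot be derived from the documents. A reader might also infer that the pneumonitis row would lose much of its content; the documents give no pneumonitis rate in support. The ORR analysis is unaffected.

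The change is worth making because the rules are stated, would mis-sort events if followed, and are cheap to correct.

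**What to change.** In SAP Appendix 1:

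1. **Pneumonia:** limit the string rule to the infections SOC, keep the aspiration exception, and state that the remaining named terms are additions.
2. **All infections:** exclude every term in the Pneumonia group and every term in the COVID-19 group, both by membership. Because this replaces the word-based exclusion, state explicitly where *Pneumonia aspiration* belongs.
3. **COVID-19 pneumonia:** assign it to one row, or declare the overlap and show Pneumonia with and without it.
4. **Pneumonitis:** review the reported terms containing pneumonia or pneumonitis outside the infections SOC, except aspiration, and assign them through a fixed list settled before database lock. A reviewed list is preferable to a second open string rule.

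The cost is a small edit to the appendix and the lookup table, with no new data. The AESI rows may become slightly less comparable with earlier duvelisib summaries if those used the present grouping, which the documents do not say.

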Febrile neutropenia	Grade 3-4	
 • Interrupt duvelisib until afebrile and resolution of Grade 3 or Grade 4 neutropenia to Grade ≤ 2
Neutropenia	ANC 0.5 to 1.0 Gi/L	
 • Maintain duvelisib dose • Monitor ANC at least weekly
	ANC less than 0.5 Gi/L	
 • Withhold duvelisib • Monitor ANC until > 0.5 Gi/L • Resume duvelisib at same dose (first occurrence) or at a reduced dose for subsequent occurrence (see Table 8)

Toxicity	Adverse Reaction Grade	Recommended Management
Thrombocytopenia	Platelet count 25 to < 50 Gi/L (Grade 3) with Grade 1 bleeding	
 • No change in dose • Monitor platelet counts at least weekly
	Platelet count 25 to < 50 Gi/L (Grade 3) with Grade 2 bleeding or Platelet count < 25 Gi/L (Grade 4)	
 • Withhold duvelisib • Monitor platelet counts until ≥ 25 Gi/L and resolution of bleeding (if applicable) • Resume duvelisib at same dose (first occurrence) or resume at a reduced dose for subsequent occurrence (see Table 8)

Abbreviations: ALT: alanine aminotransferase; ANC: absolute neutrophil count; AST: aspartate transaminase; CMV: cytomegalovirus; DRESS: drug reaction with eosinophilia and systemic symptoms; Gi: 1×10^9 ; PCR: polymerase chain reaction; PJP: *Pneumocystis jiroveci* pneumonia; SJS: Stevens-Johnson syndrome; TEN: toxic epidermal necrolysis; ULN: upper limit of normal.

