8.3.3. Reporting of Adverse Events and Serious Adverse Events

The AE reporting period begins from the time that the subject signs the ICF through and including 30 calendar days after the last study intervention dose. All subjects with treatment-related AEs/SAEs should be observed until resolution or stabilization. Any SAE occurring after the reporting period must be promptly reported if a causal relationship to the investigational drug is suspected. If the subject begins a new anticancer therapy, the safety reporting period ends at the time the new treatment is started, however, death must always be reported if it occurs during the AE reporting period irrespective of intervening treatment.

Elective or previously scheduled hospitalizations for pre-existing conditions that have not worsened after initiation of treatment should not be classified as SAEs. For example, an admission for a previously scheduled ventral hernia repair would not be classified as an SAE.

All AEs should be recorded individually unless, in the opinion of the Investigator or designated physician, the AEs constitute components of a recognized condition, disease, or syndrome. In the latter case, the condition, disease, or syndrome should be reported rather than each individual sign or symptom. If a constellation of signs and/or symptoms cannot be medically characterized as a single diagnosis or syndrome at the time of reporting, each individual event should be recorded as an AE or SAE as appropriate on the relevant form(s) (SAE Report Form and/or AE CRF). If a diagnosis is subsequently established, it should be reported as follow-up information becomes available. If a diagnosis is determined after the reporting of the constellation of symptoms, the signs/symptoms should be updated to reflect the diagnosis.

Each AE will be evaluated for duration, severity, seriousness, and causal relationship to the investigational drug. The action taken with study intervention and the outcome must also be recorded.

All SAEs, regardless of relationship to the study intervention, must be reported immediately (within 24 hours of awareness of event by Investigator) to the Sponsor and Contract Research Organization (CRO) pharmacovigilance group. Initial SAE notification should be made by e-mailing or faxing the SAE report form to the e-mail or fax number provided on the SAE report form.

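### The Neutropenia AESI group in SAP Appendix 1 does not include febrile neutropenia, so those events are left out of the grouped neutropenia AESI summaries

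*SAP*

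**What the plan says.** Protocol 9.4.4 leaves the definition of AESIs to the SAP. SAP 4.11.2.1 names Neutropenia as one of them and points to the appendix for its content: "The specific PTs that will be combined for each risk are defined in" Appendix 1. In that appendix the Neutropenia row reads, in full, "Neutropenia, Neutrophil count decreased". It has no string or wildcard rule. The Pneumonia row of the same table does have one: it takes in terms containing that word, with a stated exception.

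The summaries that depend on the list are wide. SAP 4.11.2.1 states: "For each risk, PTs will be summarized at the grouped PT and individual PT". It then lists subject-level rows (all grades, treatment-related, Grade 1-2 only, Grade 3 or higher, serious, holds, reductions, discontinuation, time to onset) and event-level summaries (dose modifications, outcome, duration, treating medications).

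Protocol Table 5 (Section 6.6.2) gives febrile neutropenia its own hematologic row, at Grade 3-4, with the instruction "Interrupt duvelisib until afebrile and resolution of Grade 3 or Grade 4 neutropenia to Grade ≤ 2". Neutropenia defined by neutrophil count is a separate entry, which includes "ANC less than 0.5 Gi/L". On recording, Protocol 8.3.3 says that when the Investigator or designated physician judges events to be parts of a recognized syndrome, "the condition, disease, or syndrome should be reported rather than each individual sign or symptom".

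**The concern.** The protocol recognizes febrile neutropenia as a distinct reaction, always Grade 3-4 in Table 5, that leads to interruption. The SAP group meant to characterize the neutropenia risk does not collect it. The omission is selective: it falls on the Grade 3 or higher and dose-hold rows rather than on mild events.

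This matters because neutropenia is an identified risk (Protocol 2.3.1, 34.7% in the pooled monotherapy data). Protocol 4.2 also asks whether the drug holidays reduce how often adverse events occur, how severe they are and how long they last. A reader taking the neutropenia AESI table as the full answer for this risk would not see the febrile events there, and nothing in the SAP says that they sit elsewhere.

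**Working it through.** This is mainly a check of text, followed by a simple scale calculation. The plan states no figure of its own to reproduce.

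**1. Apply the list as written (exact match on preferred term).**

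| Preferred term | In the Neutropenia row? | Would a string rule on *neutropenia* catch it? |
|---|---|---|
| Neutropenia | Yes | Yes |
| Neutrophil count decreased | Yes | No |
| Febrile neutropenia | No | Yes |

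**2. Look for the term elsewhere.** The SAP does not mention febrile neutropenia, and no other Appendix 1 row names it. The infections row takes all terms in its system organ class with exclusions. Even if coding placed febrile neutropenia there, it would be counted as an infection and not under Neutropenia.

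**3. Follow a subject through SAP 4.11.2.1.**
- *Febrile neutropenia is the only neutropenia term.* The subject is absent from every subject-level neutropenia AESI row, and the event is absent from the event-level summaries.
- *A listed term is also recorded.* The subject counts at subject level on the strength of that listed event. The febrile event itself is still missing from the event-level counts of holds, reductions, discontinuations and outcomes, and from duration and treating medications. A row with a condition, such as Grade 3 or higher, includes the subject only if the listed event meets that condition.
- *Afebrile severe neutropenia coded to a listed term.* This is fully captured, including counts below 0.5 Gi/L.

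**4. Scale.** The planned arm size is 51 (Protocol 4.1 and 9.2). Let k be the number of subjects in an arm with febrile neutropenia and no listed term. The shortfall in that arm's AESI rate is 100 × k/51 percentage points, if all 51 are dosed:

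| k (assumed) | Shortfall |
|---|---|
| 1 | 100 × 1/51 = 2.0 points |
| 2 | 100 × 2/51 = 3.9 points |
| 3 | 100 × 3/51 = 5.9 points |

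The documents give no febrile neutropenia rate. The values of k are illustrations, and k = 0 is possible.

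**The case against.** The best case for leaving the list alone has four parts.

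**The events are reported anyway.** SAP 4.11.2 tabulates treatment-emergent events by system organ class and preferred term, with separate tables for Grade 3 or higher, serious events, dose holds, reductions and discontinuations. Febrile neutropenia would have its own line in each relevant table. SAP 4.11.4 also tabulates worst on-treatment laboratory grades, including neutrophils, whatever adverse event term the site chose. This stands. A reader might infer that the events vanish from the report, but only the grouped roll-up lacks them.

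**Severe neutropenia is still in the AESI.** A reader might also infer that the most serious neutropenia events drop out of every neutropenia AESI count. The documents do not support that. Afebrile events with counts below 0.5 Gi/L, coded to a listed term, remain in the Grade 3 or higher, serious and dose-hold rows as applicable. Neither document ranks them against febrile neutropenia.

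**Sites may record both terms.** The syndrome rule in Protocol 8.3.3 depends on the judgment of the Investigator or designated physician. Protocol 8.3.6 lists severity above Grade 2, and a change or suspension of treatment, as factors that may make a laboratory finding an adverse event. Some subjects with febrile neutropenia will therefore probably carry a listed term too. This stands as a limit on size: a listed term is neither ruled out nor assured.

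**A narrow group may be deliberate.** Table 5 separates the two reactions, and the identified risk is called simply neutropenia. The terms behind the pooled 34.7% are not given, so a wider group might not match it. The SAP gives no such rationale, however, and the comparability loss is speculative. The individual-term lines that SAP 4.11.2.1 already requires would keep the current two terms visible.

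Comparing this row with others that include severe forms (hepatic failure, toxic epidermal necrolysis, necrotising colitis) adds some weight, but it is not proof of error: the rows do not follow one stated rule.

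**Conclusion.** The omission is certain on the text: febrile neutropenia coded to its own preferred term is outside the Neutropenia AESI group and its grouped summaries. The size is 2.0 percentage points of an arm's rate per subject with no listed term, and the number of such subjects is unknown. It would be wrong to state that the rates will be understated in both arms, because that depends on such subjects occurring.

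The conclusion assumes that the coding dictionary assigns these reports to a separate febrile neutropenia term and that Appendix 1 is applied literally. It concerns descriptive safety tables only. Under Protocol 9.4.1 there is no formal testing of safety data and no formal comparison of arms, no decision rule uses an AESI rate, and the primary response-rate analysis is untouched. It is a modest definitional gap, worth closing because closing it costs almost nothing.

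**What to change.** In SAP Appendix 1, change the Neutropenia row to: Neutropenia, Neutrophil count decreased, Febrile neutropenia. Show Febrile neutropenia as its own line under the group, as SAP 4.11.2.1 already provides for individual preferred terms. The lines for the two current terms then remain readable beside the wider group.

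The cost is one added term and a rerun of the neutropenia AESI outputs. No new data are needed and no treatment rule changes. The AESI definitions have been revised late before: SAP version 2.1 added the COVID-19 group. The one downside is that the reported neutropenia AESI rate may rise slightly and may compare less directly with figures built on a narrower set of terms.
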